8.1 Definitions

8.1.1 Adverse Event

An adverse event (AE) is any symptom, sign, illness or experience that develops or worsens in severity during the course of the study. Intercurrent illnesses or injuries should be regarded as adverse events. Abnormal results of diagnostic procedures are considered to be adverse events if the abnormality:

- results in study withdrawal
- is associated with a serious adverse event
- is associated with clinical signs or symptoms
- leads to additional treatment or to further diagnostic tests
- is considered by the investigator to be of clinical significance

For FDA regulated studies the FDA defines an adverse event as the following:

Unanticipated adverse device effect is any serious adverse effect on health or safety, any life-threatening problem or death caused by, or associated with a device, if that effect, problem, or death was not previously identified in nature, severity, or degree of incidence in the application; or any other unanticipated serious problem associated with a device that relates to the rights, safety, or welfare of subjects.

8.1.2 Serious Adverse Event

Serious Adverse Event

Adverse events are classified as serious or non-serious. A serious adverse event is any AE that is:

- fatal
- life-threatening
- requires or prolongs hospital stay
- results in persistent or significant disability or incapacity
- a congenital anomaly or birth defect
- an important medical event

Important medical events are those that may not be immediately life threatening, but are clearly of major clinical significance. They may jeopardize the subject, and may require intervention to prevent one of the other serious outcomes noted above. For example, drug overdose or abuse, a seizure that did not result in in-patient hospitalization, or intensive treatment of bronchospasm in an emergency department would typically be considered serious.

All adverse events that do not meet any of the criteria for serious should be regarded as non-serious adverse events.

8.1.3 Unanticipated Problems Involving Risk to Subjects or Others

Any incident, experience, or outcome that meets all of the following criteria:

- Unexpected in nature, severity, or frequency (i.e. not described in study-related documents such as the IRB-approved protocol or consent form, the investigators brochure, etc.)
- Related or possibly related to participation in the research (i.e. possibly related means there is a reasonable possibility that the incident experience, or outcome may have been caused by the procedures involved in the research)
- Suggests that the research places subjects or others at greater risk of harm (including physical, psychological, economic, or social harm).

8.1.4 Preexisting Condition

A preexisting condition is one that is present at the start of the study. A preexisting condition should be recorded as an adverse event if the frequency, intensity, or the character of the condition worsens during the study period.

8.1.5 General Physical Examination Findings

At screening, any clinically significant abnormality should be recorded as a preexisting condition. At the end of the study, any new clinically significant findings/abnormalities that meet the definition of an adverse event must also be recorded and documented as an adverse event.

8.1.6 Post-study Adverse Event

All unresolved adverse events considered probably or definitely related should be followed by the investigator until the events are resolved, the subject is lost to follow-up, or the adverse event is otherwise explained. At the last scheduled visit, the investigator should instruct each subject to report any subsequent event(s) that the subject, or the subject's personal physician, believes might reasonably be related to participation in this study.

8.1.7 Hospitalization, Prolonged Hospitalization or Surgery

Any adverse event that results in hospitalization or prolonged hospitalization should be documented and reported as a serious adverse event unless specifically instructed otherwise in this protocol. Any condition responsible for additional surgery should be documented as an adverse event if the condition meets the criteria for an adverse event.

Neither the condition, hospitalization, prolonged hospitalization, nor surgery are reported as an adverse event in the following circumstances:

- Hospitalization or prolonged hospitalization for diagnostic or elective surgical procedures for a preexisting condition. Surgery should not be reported as an outcome of an adverse event if the purpose of the surgery was elective or diagnostic and the outcome was uneventful.
- Hospitalization or prolonged hospitalization required to allow efficacy measurement for the study.
- Hospitalization or prolonged hospitalization for therapy of the target disease of the study, unless it is a worsening or increase in frequency of hospital admissions as judged by the clinical investigator.

8.2 Recording of Adverse Events

At each contact with the subject, the investigator will seek information on adverse events by specific questioning and, as appropriate, by examination. Information on all adverse events will be recorded immediately in the source document, and also in the appropriate adverse event case report form (CRF). All clearly related signs, symptoms, and clinically significant abnormal diagnostic procedures results should be recorded in the source document, though should be grouped under one diagnosis.

All adverse events occurring during the study period (consent through 30 day follow up) will be recorded. The clinical course of each event will be followed until resolution, stabilization, or until it has been determined that the study intervention or participation is not the cause. Serious adverse events that are still ongoing at the end of the study period will be followed up to determine the final outcome. Any serious adverse event that occurs after the study period and is considered to be possibly related to the study intervention or study participation will be recorded and reported immediately.

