3.2.2 Secondary Study Endpoints

1. Viral load measured in nasopharyngeal swab by Cycle Threshold at 0, 24, 48, and 72 hours after initiation of core warming
2. Duration of mechanical ventilation
3. Mortality

4 Study Population and Duration of Participation

All patients will have a diagnosis of COVID-19 requiring mechanical ventilation. Duration of intervention will be 72 hours. Follow-up will be to 30 days.

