5.3 Device Accountability

Core warming device accountability logs will be kept on file, will be completed on a regular basis, and will include product number, date of use, participant ID code, device damaged/destroyed and date of damage/destruction (including return date if applicable).

6 Schedule of Procedures and Data Extraction

Study Phase	Screening	Randomization/ Intervention Phase		Follow up
Study Days	Day -1to 0	Day 0	Day 1-2	Day 30
Informed Consent	X			
Review Inclusion/Exclusion Criteria	X			
Demographics	X			
Medical History/Interim History*	X			X
Physical Examination*	X		X	X
Vital Signs: Temperature, BP, HR, RR*	X	X	X	X
Height and Weight	X			
Pregnancy Test	X			
Clinical Labs	X	X	X	
Respiratory tract viral load		X	X	
Ventilator settings	X	X	X	
SOFA score	X	X	X	
Clinical Imaging (per routine)	X	X	X	
Prior/Concomitant Medications	X			X
Randomization		X		
Temperature monitoring		X	X	
PaO ₂ , FiO ₂ , parameter recording		X	X	
Adverse Event / Unanticipated Problems Assessment		X	X	X

* Interim medical history, physical exam, and vitals will be collected via chart review from routine clinical care.

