6.2 Study Visits & Data Collection

6.2.1 Screening, Enrollment, and Randomization

Study personnel will assess each subject against each inclusion and each exclusion criterion and the Investigator will determine the subject's eligibility for study participation. The principal

investigator or documented members of the research team will discuss the underlying rationale for the study, the procedures to be followed, the potential benefits and risks, and other issues mandated by the consent process with the surrogate or legally authorized representative. The participant's surrogate or legally authorized representative will be asked if they would like to participate, and if so, this will be documented using the study ICF. Determining the eligibility for each participant will require information generated during the course of routine clinical care as dictated by their attending physicians. Selected testing data will be collected in order to characterize the type, cause and severity of the patient's need for mechanical ventilation and the treatments received prior to enrollment. The data will include information from the evaluations listed below.

Once the Investigator has reviewed and signed the eligibility checklist, the research staff will enter the participant's information into the RedCap system to obtain the randomization assignment.

Data collection:

- Inclusion/Exclusion criteria review
- Study Informed Consent
- Collect Demographics (including sex/gender, race, ethnicity, and age via date of birth)
- Medical Record Review (including any history of disease, social history, physical exam findings and physicians notes)
- Review of Concurrent Medications
- Physical Exam
- Vital Signs: temperature, blood pressure, heart rate, respiration rate, height and weight
- Routine Clinical Labs/Phlebotomy such as a complete blood count (CBC) and chemistry profiles, along with most recent arterial blood gas for determination of PaO₂, if collected as routine care.
- Specific labs recorded include: sodium, potassium, creatinine, hematocrit, white blood cell count, and CRP, if collected as routine care.
- Lower respiratory tract (tracheal aspirate, sputum) viral load (cycle threshold)
- SOFA score
- Ventilator settings
- Pregnancy test for women of childbearing potential
- Randomization
- Adverse Event/Unanticipated Problem assessment and recording

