11.1 Risks

Risks of the study procedures are described below:

Core warming risks: Placement of the core warming device, similar to any device in the esophagus, can result in or exacerbate esophageal tissue damage, particularly in patients with known esophageal deformity or evidence of esophageal trauma. These risks are similar to those who receive the standard of care orogastric or nasogastric tubes inserted into the esophagus during routine clinical care of ICU patients.

There is also a risk that placement of the core warming device may result in movement of the tongue to the side, which can persist after removal; however, it is unclear whether this tongue deviation is caused by the endotracheal tube used during mechanical ventilation or if it is part of the disease progression of COVID-19 infection. Tongue deviation is one of the known sequelae of infection with SARS-CoV-2, better known as COVID-19.[53][54][55] Electromyography of the muscles innervated by the pharyngeal, superior laryngeal, and recurrent laryngeal branches of the vagus nerve, and by the accessory and hypoglossal nerves, have shown asymmetric patterns of acute or chronic neurogenic damage, or both.[54] Whether these findings reflect the direct (viral) or indirect (immune-mediated) effect of SARS-CoV-2 remains to be established.[54]

Loss of Confidentiality Risks: There is the potential for loss of confidentiality during data collection.

Temperature modulation risks: Warming critically ill septic patients has been previously investigated, with no unforeseen risks identified. Whole-body hyperthermia (to core body temperatures $> 39.0^{\circ}\text{C}$) has been tested in sedated patients undergoing colorectal surgery, as well as in oncological patients in combination with radiotherapy and/or chemotherapy.[52] Patients in these studies suffered no serious hyperthermia-related side effects despite being warmed to temperatures much higher than targeted in this study.

Potential adverse effects of external warming/body temperature elevation include:

- (1) Vasodilation of arteriovenous shunts in the skin resulting in decreased blood pressure and an increase in vasopressor dose
- (2) Elevated heart rate
- (3) Increased respiratory rate
- (4) Increased metabolic rate
- (5) Patient discomfort
- (6) Sweating
- (7) Worsened long-term neurological function in patients with acute stroke or post-cardiac arrest
- (8) Exacerbation of multiple sclerosis symptoms

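### Tongue deviation and esophageal injury, named as device risks in section 11.1, have no standard check applied alike in both arms, so adverse event counts by arm may be incomplete and unequally detected

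*Combined protocol and SAP*

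**What the plan says.** **How events are found.** Under section 8.2, at each contact "the investigator will seek information on adverse events by specific questioning and, as appropriate, by examination". Section 4 states: "All patients will have a diagnosis of COVID-19 requiring mechanical ventilation". Consent comes from a surrogate or representative (sections 3.1.1 and 4.3). The footnote to the section 6 schedule says: "Interim medical history, physical exam, and vitals will be collected via chart review from routine clinical care". Sections 5.2 and 8.6 leave the physicians and study team unblinded.

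**Which harms are named.** Section 11.1 says that placing the device "can result in or exacerbate esophageal tissue damage, particularly in patients with known esophageal deformity or evidence of esophageal trauma", and that it "may result in movement of the tongue to the side, which can persist after removal". On the cause of the second, "it is unclear whether this tongue deviation is caused by the endotracheal tube used during mechanical ventilation" or is part of COVID-19. The listed effects of raised body temperature include "4) Increased metabolic rate".

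**What is scheduled.** Physical examination is ticked at screening, Day 1-2 and Day 30, and adverse event assessment at Day 0, Day 1-2 and Day 30. The device stays in for 72 hours (section 5.1), but no column stands for hour 72 or for removal. Neither the schedule nor the lists in 6.2.1 to 6.2.3 contain a tongue, esophageal or upper-airway check. Sections 6.2.1 and 6.2.2 mention the blood gas only as the "most recent arterial blood gas for determination of PaO₂, if collected as routine care".

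**The concern.** While the device is in place patients are ventilated, so questioning them will yield little. Examination is discretionary, and the charted examination is whatever routine care recorded. Staff who know the arm may look harder around the device and find more there. They may also attribute a finding to COVID-19, which section 11.1 already offers as an explanation. The bias could run either way, and the plan has nothing that would show its direction.

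The gap matters most for tongue deviation. Section 11.1 leaves open whether the tube or the disease is responsible. Controls have both but not the device, so the randomized arms are the comparison that bears on the question, provided both are looked at in the same way and at the same times. Section 6.2.2 is headed by reference to placement, a moment that controls do not have.

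The decision to continue after 10 patients (section 7.3.2) and the final safety statement both rest on this record. Bedside findings that nobody looked for cannot be recovered later.

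**Working it through.** The plan gives no adverse event rate, capture rate, alpha or power, so there is no figure of its own to reproduce. From the documents: 11 per arm (section 3.1), a safety review after 10 enrolled (section 7.3.2), and chi-squared or Fisher tests for categorical data (section 7.3). My assumptions: the true event rates *r*, the share of cases noticed *s*, 5 warmed patients at the interim (an even split), and a two-sided 0.05 level.

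**1. Incomplete detection in the device arm.** The chance of recording at least one case among *n* patients is 1 − (1 − *r·s*)^*n*.

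| *n* | True rate | All cases found | Half found |
|---|---|---|---|
| 11 | 5% | 43% | 24% |
| 11 | 10% | 1 − 0.90^11 = 69% | 1 − 0.95^11 = 43% |
| 11 | 20% | 1 − 0.80^11 = 91% | 1 − 0.90^11 = 69% |
| 5 | 10% | 41% | 23% |
| 5 | 20% | 1 − 0.80^5 = 67% | 1 − 0.90^5 = 41% |

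**2. Unequal detection between arms.** Suppose the device has no effect and the true rate is the same in both arms. If 80% of device cases and 20% of control cases are noticed, a true rate of 30% appears as 0.30 × 0.80 = 24% against 0.30 × 0.20 = 6%. From two binomials of 11, the device arm shows more cases in 82% of trials, against 40% if 80% are noticed in both arms. At a true rate of 20% the figures are 72% and 38%; at 50%, 93% and 41%.

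Reversing the two shares makes the control arm look worse equally often. A real excess can also vanish: true rates of 40% and 10%, with 25% of device cases and all control cases recorded, give 0.40 × 0.25 = 10% in each arm.

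**3. What full detection cannot do at this size.**
- With no cases among 11 controls, Fisher's test needs 5 of 11 device cases (p = 0.035); 4 of 11 gives p = 0.090.
- For true rates of 40% and 10%, raising capture from half to all in both arms lifts exact power only from 3% to 19%. For 60% and 10% it rises from 13% to 56%.
- No event in 11 is compatible with a true rate up to 1 − 0.025^(1/11) = 28% (exact two-sided 95% limit). No event in 5 is compatible with 1 − 0.025^(1/5) = 52%. Better checking leaves these limits unchanged; it only makes the zero believable.

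**4. Metabolic rate.** Temperature (expressly in both arms, section 3.1.2), heart rate and respiratory rate are recorded and give indirect signals, although the ventilator may set the respiratory rate. PaCO2 and pH, which would add to these when read with minute ventilation, are not named for extraction, while PaO2 from a blood gas is.

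**The case against.** The plan does collect adverse events in both arms. Assessment is scheduled without distinction by arm, all events from consent to Day 30 are recorded (section 8.2), and every randomized subject contributes to the safety analysis (section 7.3.2). Section 8.2 provides for examination and for significant abnormal diagnostic results. Section 8.1.5 requires new findings at the end of the study to be logged, and section 4.3 foresees patients regaining capacity, so some can answer questions later. All of this stands. A reader might infer that the control group cannot show what the device causes; these provisions do not support that. The comparison is weakened and open to detection bias, but it exists.

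It is also fair to say that full detection would not let 11 per arm settle causation; step 3 above confirms it. Section 11.1 likens the esophageal risk to that of standard gastric tubes, so if controls have such tubes, the esophageal contrast is device against tube. A checklist would not blind the staff either, although fixed items at fixed times leave less room for selective looking. Finally, the laboratory lists are open-ended and the case report form is not in the documents, so PaCO2 and pH may be captured without being named.

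What remains is that the two local harms have no prompt, no fixed time and no requirement that both arms be examined alike.

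**Conclusion.** The point holds in limited form. Detection of tongue deviation and esophageal injury rests on questioning ventilated patients, discretionary examination and routine charting, all by staff who know the arm. Counts by arm may therefore be incomplete and differ for reasons unrelated to the device. Increased metabolic rate is covered by indirect signals only.

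If half of cases go unnoticed, the chance of seeing a 20% harm at least once falls from 91% to 69% among 11 warmed patients, and from 67% to 41% among 5 at the interim. With unequal capture (80% against 20%) and no true effect, the device arm shows the higher count about four times in five at a 30% rate. The event rates, the capture shares and the 5 warmed patients at the interim are assumptions; the documents supply none of them. The figures show how sensitive the record is, and do not predict what will be seen.

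This is an inexpensive improvement to a pilot whose data are meant to inform larger studies (section 7.2). It does not invalidate the design.

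**What to change.** 1. **Sections 6 and 8.2:** add a short solicited checklist (tongue deviation; signs of esophageal or upper-airway injury), each item recorded as present, absent or not done. Complete it at baseline, hour 72 and Day 30 in both arms, with times counted from randomization. The baseline check separates preexisting findings from new ones; the not-done category shows where death, discharge or withdrawal left a gap.
2. **Sections 6.2.1 and 6.2.2:** name PaCO2 and pH for extraction from the same gases as PaO2, and minute ventilation where the ventilator record gives it.
3. **Sections 7.3.2 and 7.4:** tabulate these items by arm, with the number examined and exact confidence intervals, for all randomized patients at the 10-patient review and at the end. Section 7.4 now limits analysis to patients who completed the study, so exempt the safety tables from that limit. State that 11 per arm gives descriptive estimates only.

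Cost: a one-page form, a brief bedside look three times per patient and a few extra data fields. The Day 30 look is the least convenient, because that examination now comes from the chart and a discharged patient would need a contact or be recorded as not done.

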3.1 General Design

This is a small scale pilot study to evaluate if core warming improves respiratory physiology of mechanically ventilated patients with COVID-19, allowing earlier weaning from ventilation, and greater overall survival. This prospective, randomized study will include 22 patients diagnosed with COVID-19, and undergoing mechanical ventilation for the treatment of respiratory failure. Patients will be randomized in a 1:1 fashion with 11 patients (Group A) randomized to undergo core warming, and the other 11 patients (Group B) serving as the control group who will not have the ensoETM device used. Patients randomized to Group A will have core warming initiated in the ICU or other clinical environment in which they are being treated after enrollment and provision of informed consent from appropriate surrogate or legally authorized representative.

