8.5.1 Follow-up report

If an SAE, UP or Unanticipated Adverse Device Effect has not resolved at the time of the initial report and new information arises that changes the investigator's assessment of the event, a follow-up report including all relevant new or reassessed information (e.g., concomitant medication, medical history) should be submitted to the IRB. The investigator is responsible for ensuring that all events are followed until either resolved or stable.

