8.6 Unblinding Procedures

The study team will not be blinded to the randomization assignment. The study team will be instructed to maintain blinding for participants unless a participant has a clinical need to know their randomization assignment. The decision to unblind will be at the discretion of the study PIs and only if unblinding would change clinical care. Unblinding for safety reasons will be recorded in study records and it will be reported to the IRB and the funding sponsor at the time of continuing review.

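### Section 8.2 lets an unblinded causality judgement end follow-up of a non-serious adverse event, so its recorded course and persistence may differ by arm because of the rule

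*Combined protocol and SAP*

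**What the plan says.** Section 8.2 sets a broad recording rule: "All adverse events occurring during the study period (consent through 30 day follow up) will be recorded". It then says that an event's course is to be "followed until resolution, stabilization, or until it has been determined that the study intervention or participation is not the cause". That gives three ways to end follow-up, and the third is a judgement about cause. A separate sentence covers serious events: "Serious adverse events that are still ongoing at the end of the study period will be followed up to determine the final outcome".

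Section 3.1 describes Group B as "serving as the control group who will not have the ensoETM device used". On who makes the judgement, 8.6 states: "The study team will not be blinded to the randomization assignment". Section 5.2 says the same of the physicians.

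Two other sections bear on follow-up. Section 8.1.6 continues follow-up of unresolved events after the study only when they are rated probably or definitely related. Section 8.5.1, which concerns reports of serious events, unanticipated problems and unanticipated device effects, makes the investigator responsible for ensuring that "all events are followed until either resolved or stable". It has no causality exit.

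Section 11.1 warns that placing the device "may result in movement of the tongue to the side, which can persist after removal". It adds that the role of the endotracheal tube or of COVID-19 in this is unclear.

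**The concern.** The length of follow-up should not depend on treatment arm or on opinion about cause. Here it can depend on both, because one of the exits is a causality judgement made with the allocation known, and one arm lacks the main candidate cause.

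What is at stake is the comparison of how long non-serious harms last. For a harm that the device, the tube or the disease could each produce, the randomized control arm is how the trial can separate them. That works only if outcomes are ascertained alike in both arms. The distortion could go either way. If control events are closed as not caused by the study while Group A events stay open, persistent events will be documented mainly in Group A and the device will look worse. If Group A events are attributed to the tube or to COVID-19 and closed, lasting device harm may go undocumented.

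**Working it through.** No arithmetic settles this point, and the plan states no figure to reproduce. The check sets the sections side by side.

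1. **Which events the exit governs.** Occurrence is recorded for all events in both arms whatever the cause (8.2). Serious events still ongoing at study end are followed to final outcome with no condition on cause (8.2). What remains exposed is the course and outcome of non-serious events.

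2. **How reachable the exit is in each arm.** The clause names two things to be ruled out: the intervention and participation. Section 8.3 likewise grades relatedness against the research procedures and not the device alone.
   - Group A: both the device and the other research procedures must be ruled out.
   - Group B: the device is absent, so only participation is left. Labs, vital signs and imaging are usual care (3.1.2), examinations and vital signs are taken from the chart (section 6 footnote), and most procedures are described as standard of care (11.4). The main evident research procedure in controls is viral-load sampling.
   
   The exit is therefore easier to reach in Group B, although it is not met there automatically.

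3. **Whether other provisions recover the outcome of a closed event.**
   - 8.1.1 captures events that develop or worsen, not events that merely persist.
   - 8.1.5 asks at study end for new clinically significant findings. A persistent finding already recorded and closed is not new.
   - Section 6 and 6.2.3 schedule an adverse event assessment at Day 30 in both arms but do not require the status of events closed earlier.
   - 8.1.6 extends follow-up only for probably or definitely related events, which points the same way as the exit in 8.2.
   - 8.5.1 has no causality exit. If its sentence covers only the expedited events that the section is about, the gap for non-serious events stands. If it covers every event, it contradicts 8.2.

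4. **An example.** Tongue deviation can persist and its cause is stated to be unclear (11.1). If a case is classed as non-serious, its persistence is exposed to the exit. If it is classed as serious, 8.2 protects it.

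5. **Size.** A numerical effect would need the rate of persistent non-serious events and the share closed on causality in each arm. The documents give neither. The only scale they offer is the allocation: "Patients will be randomized in a 1:1 fashion with 11 patients (Group A) randomized to undergo core warming", with 11 controls. One patient whose outcome goes unrecorded is 1/11 = 9.1% of an arm.

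**The case against.** The strongest reply is that the Day 30 review catches what matters. History, examination and adverse event assessment are scheduled for every patient, investigators must ask about events at each contact, and worsening is itself a recordable event. A control patient with a visible persisting finding may well be noted. This stands in part: it makes loss less likely in practice. It does not close the gap, because nothing requires the status of an already closed event to be updated. Collection by chart review limits sensitivity, though in both arms alike.

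Several stronger readings are tempting, and the documents do not support them:

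- *Control events meet the exit by definition and can be closed at onset.* The clause also names participation, and controls do undergo viral-load sampling, so a judgement is still needed.
- *Follow-up will be unequal.* The rule permits this and does not require it. Resolution and stabilization apply equally to both arms, and unrelated Group A events can be closed too.
- *Adverse event counts are biased.* Occurrence is recorded regardless of cause, so incidence is not directly affected.
- *Tongue deviation is a non-serious event that the rule will miss.* Section 11.1 does not class it, and a persistent case might meet the criteria for a serious event in 8.1.2.
- *A particular false result in persistent cases can be predicted.* That would need assumed incidence and persistence rates with no source in the plan.

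It is also fair to say that no endpoint (3.2) and no specified analysis (7.3, 7.3.2) compares the duration or persistence of adverse events by arm. That limits the consequence to the descriptive safety record.

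**Conclusion.** The concern holds in a limited form. Section 8.2 allows follow-up of a non-serious event to end on an unblinded causality judgement, and that exit is easier to reach in the arm without the device. The recorded course and persistence of such events may therefore differ by arm because of the rule. The direction cannot be predicted and the size cannot be derived.

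This rests on two readings: that the sentence in 8.5.1 is confined to the expedited events its section covers, and that the Day 30 assessment does not oblige staff to revisit closed events. If 8.5.1 was meant to cover every event, the problem becomes a direct contradiction with 8.2 and still needs correction. The consequence is modest, but the change is cheap and removes an avoidable arm-dependent bias from the safety data of a trial with 11 patients per arm.

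**What to change.** In 8.2, delete the causality exit, so that every adverse event in both arms is followed at least until resolution, stabilization or the Day 30 review. Record the status of every adverse event at Day 30 in both arms, including events closed earlier. Rate relatedness separately, so that it does not control follow-up up to Day 30.

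Do not make Day 30 a cap. Section 8.2 has no such limit now, and a cap would conflict with the open-ended follow-up of related events in 8.1.6. Keep the existing longer follow-up of ongoing serious events (8.2) and of probably or definitely related unresolved events (8.1.6). Follow-up beyond Day 30 would still depend on relatedness, so any comparison of persistence between arms should use the Day 30 status. Reconcile 8.1.6, 8.2 and the sentence on all events in 8.5.1 so that they state one rule.

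The cost is an edit to these three sections, one CRF field, and a few more chart look-ups at the Day 30 review already planned for all patients.
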